Study Protocol for: Imaging della Placca Carotidea (IMPLAC) study

Funding: Italian Ministry of Health

Grant number: GR-2009-1608780

NCT number: NCT03333330

The aim of the present study will be to evaluate the relation between carotid artery plaque characteristics, cardiovascular risk factors and brain atrophy/WMH burden analyzed, quantitatively as number and volume of lesions and as brain volumes, and progression over 18 months of follow up in subjects asymptomatic for cerebrovascular disease with a carotid artery stenosis <70%. We will characterize the carotid artery plaque using ultrasound, contrast enhanced ultrasound and computed tomography angiography. Cerebral volumes and WMH were evaluated quantitatively using brain magnetic resonance imaging. All baseline imaging and clinical evaluation will be performed within one month from enrollment.

Patient enrollment

Asymptomatic subjects with carotid stenosis <70% according to Doppler velocity measurement presenting to the Neurophysiology and the Vascular Surgery outpatient clinics of Ospedale San Raffaele (Milan, Italy) will be evaluated for enrollment. Exclusion are: age <18 or > 85 years, pregnancy, history of allergic diathesis, previous stroke or transitory ischemic attack, previous carotid endarterectomy (CEA) or stenting, vasculitis, history of alcohol or drug abuse, life expectancy of <18 months, presence of cognitive impairment preventing the patient from providing informed consent, history or current AF or previous cardiac surgery as potential confounding causes of cerebral ischemic damage. These criteria were selected to limit the inclusion of potential confounding causes of cerebral damage. Table 1 provides a schematic for the exclusion criteria. All subject will have to sign a written informed consent to take part in the study.

Exclusion criteria for the IMPLAC study

Age <18 or >85 years

Contraindications to CTA (eGFR<60 mL/min; history of allergic reaction to iodinated contrast media)

Pregnancy or child-bearing potential

Specific contraindication to MRI:

- Claustrophobia
- Sickle cell anemia
- Systemic mastocytosis
- Implanted cardiac devices (PM, ICD)
- Vascular clips
- Vertebral distractors
- Infusion pumps
- Neurostimulators
- Liquor derivations
- Any device which could be dispositioned in the presence of a strong magnetic field

Dementia

Life expectancy less than study follow up (18 months)

History of drug abuse, alcohol abuse or any psychiatric or social condition which may contraindicate the participation to a clinical study

Vertebral artery occlusion
Previous revascularization of the carotid artery
Current anti-coagulation
Atrial fibrillation not necessitating anticoagulation
Known PFO necessitating anti-platelet treatment
Previous cerebrovascular accidents
Previous infections to the CNS
Previous surgery to the CNS
History of anoxic damage to the CNS
Previous cardiac surgery or positioning of intracardiac devices (excluded coronary stents)
History of autoimmune vasculitis

Table 1. Exclusion criteria for the IMPLAC study. CTA: computed tomography angiography. CNS: central nervous system. PFO: patent foramen ovale.

Clinical evaluation and biochemical measurements

At enrolment, all subjects will undergo clinical evaluation including careful medical history, and physical examination, comprising cardiac auscultation for the detection of irregular heartbeat and two blood pressure measurements. The history will be focused on the identification of cardiovascular risk factors (CVRFs) and of current treatment. Whole blood will be collected on the same day using two 5mL EDTA-anticoagulated vacutainer tubes. For each patient, glycaemia, total cholesterol, high-density lipoprotein cholesterol (HDL-C), low-density lipoprotein cholesterol (LDL-C) and triglycerides will be measured using a colorimetric method using the Cobas Mira Plus analyzer (Horiba, ABX, France).

A patient will be defined as suffering from hypertension in compliance with the definition of the European Society of Cardiology (ESC)/European Society of Hypertension, i.e. systolic blood pressure (BP) ≥ 140 mmHg or diastolic BP ≥ 90 mmHg. A clinical history of hypertension with current BP medication will also be considered diagnostic. A subject will be considered as suffering from resistant hypertension in the presence of uncontrolled hypertension or a history of poorly controlled BP and a current BP treatment with at least three drugs including a diuretic. A fasting blood glucose > 126 mg/dL, a glycaemia > 200 mg/dL two hours after an oral glucose load of 75g, HbA1C levels over 6.5% or current treatment with oral anti-diabetic agents or insulin will be taken into account for the diagnosis of diabetes. Hypercholesterolemia is defined according to ESC guidelines: total cholesterol ≥ 200 mg/dL and /or LDL-C ≥ 120 mg/dL. Current lipid lowering therapy will also be taken into consideration for the definition of hypercholesterolemia. To evaluate the cardiovascular risk profile of our patients, we employed the Framingham Risk Score (FRS) to estimate the probability of a first acute myocardial infarction at 10 years. The variables taken into consideration are age, systolic BP, current smoke, BP medication, total cholesterol and HDL-C. A patient with a FRS $> 20\%$ is considered at high risk. The presence of diabetes mellitus or manifest cardiovascular disease confer high risk independently from calculated FRS.

Carotid artery ultrasound

All patients will undergo bilateral Duplex ultrasound evaluation of the carotid arteries. Examinations will be performed using a dedicated ultrasonography equipment (Logiq S8, GE Healthcare, UK) with a 7-MHz linear probe (7L, GE). The patient is positioned supine, with the head tilted 45° toward the side opposite to the one being imaged. A transverse sweep is recorded from the lower neck to the common carotid artery (CCA) bifurcation into the external carotid artery (ECA) and internal carotid artery (ICA) in order to identify atherosclerotic lesions, defined as focal lesions exceeding 2 mm in thickness. Each of the segments is identified according to the Rotterdam Study criteria: the 15 mm caudal to the bifurcation was defined as carotid bulb, while cranially we identified ICA and ECA. Longitudinal images are then recorded using anterior, posterior and lateral (45°) views.

Common carotid intima-media thickness (CC-IMT) measurement is performed bilaterally in lateral projection images of the CCA in a semi-automated manner. Briefly, the measures performed on 350 consecutive points taken from approximately 10 mm proximal from the bulb are averaged. We carefully avoided inclusion of CCA atherosclerotic plaques in the measurement of CC-IMT. We will record the highest mean CC-IMT for each patient.

Doppler velocity measurements are made on longitudinal views at the site of any identifiable lesions within CCA, carotid bulb or ICA. The degree of stenosis is evaluated by velocimetric criteria according the Society of Radiologists in Ultrasound Consensus Conference. The plaque determining the highest stenosis is considered the main lesion. For the main lesion, we calculated the degree of stenosis according to the European Carotid Surgery Trial (ECST) criteria, as previously described. Briefly, the narrowest diameter and the estimated normal diameter of the artery at the site of the main plaque were measured, and the degree of stenosis was calculated as $[1 - (\text{narrowest diameter} / \text{estimated normal diameter})] \%$.

For each patient, Total Plaque Area (TPA) is measured off-line. Briefly, two independent operators ([name] and [name]) measured the two dimensional area of each identifiable lesion by tracking around the lesion perimeter. The sum of all lesions areas is taken as TPA. The number of segments, CCA, bulb, ICA and ECA bilaterally, involved by atherosclerosis was also registered as an indicator of the extension of the disease.

Finally, each plaque is classified according to its echogenicity, as previously described by Purcelot et al in 1999. Briefly, plaques are considered class I if they were uniformly hypoechoic, class II if they were heterogeneous, mainly hypo-echoic, class III if they were heterogeneous, mainly hyperechoic, class IV if they were uniformly iso-hyper-echoic or class V if they were hyperechoic and displayed posterior acoustic shadow. For subsequent analysis, class I and II were considered a single category, namely lipid-rich plaque, while classes III to V were considered together as fibrocalcific plaques.

Contrast enhanced ultrasound (CEUS) examination

CEUS will be performed on the same day of standard ultrasound evaluation of the carotid arteries using the same equipment. Preset contrast-specific modality (pulse inversion) is employed, adjusting image settings in order to maximize contrast signal visualization and using low mechanical index (0.08-0.12). Five ml of sodium hexafluoride (SonoVue, Bracco Imaging, Italy) were diluted 1:3 in saline. A 3 ml bolus is injected through a peripheral vein and then flushed with 5 ml saline. Plaque neovascularization will be assessed offline by 3 independent operators as previously described by Coli et al in 2008. Each lesion is graded as CEUS⁻ or CEUS⁺ depending on absence or presence of neovascularization signal, respectively. CEUS⁺ plaques were defined as plaques in which contrast bubbles, identified as moving bright spots, reached the plaque core or in which contrast signal was seen throughout the entire lesion. For each patient, the total number of neovascularized plaques will be recorded as a semi-quantitative index of neoangiogenetic activity.

Computed Tomography Angiography (CTA)

All patients will be examined with a 64-slice CT scanner (VCT Lightspeed, GE Healthcare, USA). Fifty ml of non-ionic, iso-osmolar contrast material (Iodixanol, 320 mg of iodine per millilitre, Visipaque 320; GE Healthcare, USA) prepared at 37°C will be injected into an antecubital vein through a 20 or 18-gauge catheter at a rate of 5 ml/s, followed by the injection 50 ml of saline. Contrast administration is performed using a dual-shot injector (Nemoto Kyorindo, Japan). The degree of stenosis in CCA, carotid bulb and ICA will be analyzed according to North American Symptomatic Carotid Endarterectomy Trial (NASCET) and ECST criteria. Briefly, for what concerns the NASCET method, the narrowest luminal area at the site of the stenosis and the area of normal artery distal to the plaque are measured, and the degree of stenosis was calculated as $[1 - (\text{narrowest area} / \text{normal area})] \%$. For the ECST, the method is analogous as for what is described above for duplex imaging, but areas are used instead of diameters. The axial data and multiplanar reconstruction (MPR) were used to determine the grade of stenosis, to calculate the plaque volume and the composition of the plaque, defined on the basis of plaque density in Hounsfield units (HU).

Brain magnetic resonance imaging

In all subjects, the following sequences of the brain will be collected during a single session using a 1.5 Tesla scanner (ACHIEVA Philips Medical Systems):

- Two-dimensional (2D) FLAIR (repetition time [TR]/echo time [TE]=11000/140 ms, inversion time [TI]=2800 ms, echo train length [ETL]=47, flip angle [FA]=90°, matrix size=384x253, field of view [FOV]=230x230 mm², 44 axial 3 mm-thick slices, number of excitations [NEX]=3, SENSE=1.5, acquisition time [TA]=7'20").
- 2D T2-weighted turbo spin-echo (TSE) (TR/TE=8897/100 ms, ETL=15; flip angle [FA]=90°, matrix size=384x242, FOV=230x230 mm², 44 axial 3mm-thick slices, NEX=3, SENSE=1.5, TA=4:9).
- 3D T1-weighted transient field echo (TFE) (TR/TE=7/3.2 ms, TI=900 ms, FA=8°, matrix size=256x256, FOV=256x256 mm², 192 sagittal 1.2 mm-thick slices, NEX=1, SENSE=2, TA=6'47").

FLAIR-hyperintense lesions, i.e. WMH, will be identified by consensus by two experienced observers blinded to carotid arteries CT and ultrasound evaluation. FLAIR lesion volume (LV) is quantified using a local thresholding segmentation technique (Jim 6, Xinapse Systems, West Bergholt, UK; <http://www.xinapse.com/>). FLAIR lesion volume and number is reported for the whole brain and for each hemisphere separately. Using 3D T1-weighted images, normalized total brain volumes (NBV), WM volumes (WMV) and GM volumes (GMV) will be measured using the SIENAX software. To avoid a possible bias in image segmentation due to the presence of T1-hypointense lesions, a binarized lesion mask from FLAIR lesions is created and transformed to the original space of the 3D T1-weighted image. After visual inspection and an eventual manual editing, WM lesions are refilled using the tool in FSL 5.0.5 software.

Follow up evaluation

Patients will be called for follow up evaluation after 18 months from enrolment. Follow up evaluation will comprise a clinical examination and a clinical history aimed at identifying potential relevant cardiovascular events, i.e. cerebrovascular accidents. All patients will undergo a ultrasound evaluation, CEUS and cerebral imaging using the above specified protocols.

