Milan, 1st April 2012

Statistical plan for: Imaging della Placca Carotidea (IMPLAC) study

Funding: Italian Ministry of Health

Grant number: GR-2009-1608780

NCT number: NCT03333330

The primary outcome of the study will be the presence of white matter hyperintensities (WMH) progression (defined as the appearance of at least 1 new lesion on cerebral magnetic resonance imaging) after 18 months. The secondary endpoint will be the reduction of brain volumes (total volume, grey matter volume and white matter volume) at 18 months. Our primary analysis will be focused at identifying independent predictors of WMH among clinical characteristics of the patients as well as plaque related variables, including volumetric measures of plaque volumes and characteristics of plaque vulnerability, such as presence of ulcer or neovascularization. All continuous variables will be tested for normality using Shapiro-Wilk normality test and are expressed as mean±standard deviation (SD) or median [interquartile range (Q1-Q3)] as appropriate. Categorical variables are summarized as absolute frequency (percentage). Group differences will be tested using unpaired t test, Mann-Whitney U test or Wilcoxon matched pair signed rank test. Spearman's rank correlation coefficient was used to assess statistical dependence. Association between categorical variables was tested using Chi-squared test or Fisher's exact test as appropriate. A $p<0.05$ was considered significant. A multivariate regression analysis was then performed to identify factors that independently influence the burden of WMH in terms of number and volume. All variables associating to WMH burden with a $p<0.10$ will be included in the multivariable model. Our main hypothesis is that subjects with a high plaque burden will experience the highest progression of WMH. We calculated the sample size for multivariate logistic regression analysis with a power of 0.8 and an alpha of 0.05. We will analyze the highest tertile of carotid plaques burden in terms of plaque volume versus others (see Sillesen, 2012). By this definition, the prevalence of high burden atherosclerosis will be 33%. We estimated a clinically relevant probability of progressing in terms of WMH in the high burden group to be 50%, while subjects without high burden plaques are estimated to progress in terms of WMH as the general population with carotid atherosclerosis in a similar time frame. This probability would be estimated to be around 15% (see Dufoil, 2005 and Pico, 2002). The estimated sample size would be 58 individuals. All statistical analyses will be performed using GraphPad Prism 5 (GraphPad Software Inc., La Jolla, USA), IBM SPSS Statistics 20 (IBM, Armonk, USA) or R v3.1.2.

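### Brain-volume reduction over 18 months rests on a per-scan tool (SIENAX), so measurement error enters at both visits; a paired measure of total brain volume change may be more precise

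*Protocol*

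**What the plan says.** The SAP defines the endpoint as a change: "The secondary endpoint will be the reduction of brain volumes (total volume, grey matter volume and white matter volume) at 18 months". It gives no formula for that change (absolute, percentage or baseline-adjusted).

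Under *Brain magnetic resonance imaging*, the protocol specifies the measurement on the 3D T1-weighted images: "normalized total brain volumes (NBV), WM volumes (WMV) and GM volumes (GMV) will be measured using the SIENAX software". A FLAIR-derived lesion mask is inspected, edited by hand if needed, and used for lesion filling in FSL.

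Under *Follow up evaluation*, it says: "All patients will undergo a ultrasound evaluation, CEUS and cerebral imaging using the above specified protocols".

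Neither document names a paired or registration-based volume method, a scan-rescan error, an expected 18-month volume loss or its SD. The SAP lists general tests ("Group differences will be tested using unpaired t test, Mann-Whitney U test or Wilcoxon matched pair signed rank test") but assigns none of them to brain volume.

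**The concern.** The endpoint is a within-patient change, while the only tool named measures one scan at a time. If the plan is followed as written, each patient's reduction is derived from two volumes, each with its own random segmentation and normalisation error. The lesion mask and any manual editing are specific to the visit, and the lesions themselves are expected to progress, so the two errors are unlikely to cancel completely.

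The protocol's opening paragraph sets out to relate plaque characteristics and risk factors to brain atrophy and to progression over 18 months. That compares change between patients. Random error in such an outcome widens its spread, weakens correlations and enlarges the smallest detectable difference. The study was not sized for this endpoint, so there is no stated margin to absorb the loss. A paired measurement compares the two T1 scans of the same patient directly and may avoid part of it.

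**Working it through.** **1. The plan's own figure.** The SAP states: "We calculated the sample size for multivariate logistic regression analysis with a power of 0.8 and an alpha of 0.05". Its inputs are a high-burden prevalence B = 0.33 and WMH progression probabilities of 0.50 (high burden) and 0.15 (others). I used the standard formula for logistic regression with one binary covariate, two-sided alpha (the SAP does not state sidedness) and overall event rate P = 0.67 × 0.15 + 0.33 × 0.50 = 0.2655:

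N = [1.96·√(P(1−P)/B) + 0.84·√(0.15·0.85 + 0.50·0.50·0.67/0.33)]² / [(0.35)²·0.67] = 57.8, hence 58.

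The stated sample size reproduces. It concerns WMH progression only and does not depend on how brain volume is measured.

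**2. Error of a change score.** Let σ be the single-visit error SD, ρ the correlation of the errors between visits, d the SD of true change between patients and s the error SD of a paired measure, all in % of volume.

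- Error variance of a two-visit change: 2σ²(1−ρ)
- Variance of observed change, two visits: d² + 2σ²(1−ρ)
- Variance of observed change, paired: d² + s²

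**3. Assumed inputs.** None is in the documents: d = 0.5-0.7, s = 0.2-0.3, σ = 0.2-1.0, ρ = 0 or 0.5.

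| d | σ | ρ | s | Two-visit variance | Paired variance | Ratio |
|---|---|---|---|---|---|---|
| 0.7 | 0.2 | 0 | 0.3 | 0.57 | 0.58 | 0.98 |
| 0.5 | 0.2 | 0 | 0.2 | 0.33 | 0.29 | 1.14 |
| 0.7 | 0.5 | 0.5 | 0.3 | 0.74 | 0.58 | 1.28 |
| 0.7 | 0.5 | 0 | 0.3 | 0.99 | 0.58 | 1.71 |
| 0.5 | 1.0 | 0.5 | 0.2 | 1.25 | 0.29 | 4.31 |
| 0.5 | 1.0 | 0 | 0.2 | 2.25 | 0.29 | 7.76 |

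**4. Illustrative group contrast.** The highest plaque tertile against the rest gives about 0.33 × 58 = 19 vs 39. The detectable difference with 80% power is 2.80 × SD × √(1/19 + 1/39) = 0.783 × SD.

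- Two visits, ρ = 0, σ = 0.5-1.0: SD from √(0.25 + 0.50) = 0.87 to √(0.49 + 2.00) = 1.58; detectable 0.68 to 1.24 percentage points.
- Paired: SD from √(0.25 + 0.04) = 0.54 to √(0.49 + 0.09) = 0.76; detectable 0.42 to 0.60 percentage points.

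**5. Mean decline in the whole cohort.** Assume a mean loss of 0.75%, d = 0.5, ρ = 0 and 58 patients. At σ = 1.0 the SD is √(0.25 + 2.00) = 1.50, the standard error 1.50/√58 = 0.197, and power about 97%. At σ = 1.5 it is about 75%. The overall decline is therefore fairly robust, and the loss falls mainly on between-patient contrasts.

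**The case against.** The strongest case against the point is that its size comes entirely from assumed error values. That stands. The same patient is imaged with the same sequences and software, so the errors may be positively correlated. If single-visit error is as low as 0.2%, the gain vanishes. Adding a correlation of 0.5 can reverse it: with d = 0.5 and s = 0.3 the ratio is (0.25 + 0.04)/(0.25 + 0.09) = 0.85. At σ = 0.5 and s = 0.3, however, the advantage disappears only when 2 × 0.25 × (1−ρ) = 0.09, that is ρ = 0.82.

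Four stronger readings are tempting, and the documents do not support them:

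- *The plan prescribes subtracting two separately normalised volumes.* Neither the subtraction nor re-estimated normalisation at follow-up is stated. Both are inferred from SIENAX being the only volumetry named. What the text supports is that change must rest on two per-visit values.
- *Error will swamp the change.* With independent errors, the error SD of an individual change exceeds the mean change only when σ is above about 0.71 times that change (1/√2). The documents give neither quantity.
- *The secondary endpoint is underpowered at 19 vs 39.* The SAP uses the tertile split to size WMH progression and does not assign it to brain volume. The contrast in the working is an illustration.
- *Head-size scaling should be fixed at its baseline value.* Adult head size is stable, but scaling estimated at each visit may absorb drift in scanner calibration over 18 months. Fixing it could turn that drift into apparent volume change.

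It is also fair to say that a paired measure of total brain volume leaves grey and white matter change as two-visit differences, so the remedy is partial.

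**Conclusion.** The point holds as a modest design improvement to the secondary endpoint. The plan names a per-scan tool for a change endpoint, so random error enters at both visits. The consequence is lost precision in relating volume loss to plaque burden or other predictors. It is not bias in the mean change, and the primary endpoint is unaffected.

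The size is uncertain. Relative to a paired measure, the variance ratio runs from no gain (small single-visit error) through about 1.3 (moderate, correlated error) to 7.8 (large, independent error). Quoting only the upper part of that range would overstate what is known. The conclusion rests on the assumed SD of true change, on both error sizes and on the between-visit error correlation. A scan-rescan estimate from the study scanner would narrow it.

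**What to change.** Add a sentence to *Brain magnetic resonance imaging* stating that change in total brain volume will be measured with a paired registration-based method (for example SIENA) on the baseline and 18-month 3D T1 scans. Keep SIENAX for baseline volumes and for grey and white matter. In the SAP, define how each change is expressed and give the assumed measurement error and the detectable difference with 58 patients.

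A fixed baseline head-size scaling factor for both visits should not be part of the main analysis. If used at all, it belongs in a sensitivity analysis.

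The scans are already planned at both visits and FSL is already in use for lesion filling, so no extra visit or imaging is needed. The cost is some re-processing, and changes in total volume and in tissue volumes would come from different tools, so the two need not agree exactly.

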Milan, 1st April 2012

Statistical plan for: Imaging della Placca Carotidea (IMPLAC) study

Funding: Italian Ministry of Health

Grant number: GR-2009-1608780

NCT number: NCT03333330

The primary outcome of the study will be the presence of white matter hyperintensities (WMH) progression (defined as the appearance of at least 1 new lesion on cerebral magnetic resonance imaging) after 18 months. The secondary endpoint will be the reduction of brain volumes (total volume, grey matter volume and white matter volume) at 18 months. Our primary analysis will be focused at identifying independent predictors of WMH among clinical characteristics of the patients as well as plaque related variables, including volumetric measures of plaque volumes and characteristics of plaque vulnerability, such as presence of ulcer or neovascularization. All continuous variables will be tested for normality using Shapiro-Wilk normality test and are expressed as mean±standard deviation (SD) or median [interquartile range (Q1-Q3)] as appropriate. Categorical variables are summarized as absolute frequency (percentage). Group differences will be tested using unpaired t test, Mann-Whitney U test or Wilcoxon matched pair signed rank test. Spearman's rank correlation coefficient was used to assess statistical dependence. Association between categorical variables was tested using Chi-squared test or Fisher's exact test as appropriate. A $p<0.05$ was considered significant. A multivariate regression analysis was then performed to identify factors that independently influence the burden of WMH in terms of number and volume. All variables associating to WMH burden with a $p<0.10$ will be included in the multivariable model. Our main hypothesis is that subjects with a high plaque burden will experience the highest progression of WMH. We calculated the sample size for multivariate logistic regression analysis with a power of 0.8 and an alpha of 0.05. We will analyze the highest tertile of carotid plaques burden in terms of plaque volume versus others (see Sillesen, 2012). By this definition, the prevalence of high burden atherosclerosis will be 33%. We estimated a clinically relevant probability of progressing in terms of WMH in the high burden group to be 50%, while subjects without high burden plaques are estimated to progress in terms of WMH as the general population with carotid atherosclerosis in a similar time frame. This probability would be estimated to be around 15% (see Dufoil, 2005 and Pico, 2002). The estimated sample size would be 58 individuals. All statistical analyses will be performed using GraphPad Prism 5 (GraphPad Software Inc., La Jolla, USA), IBM SPSS Statistics 20 (IBM, Armonk, USA) or R v3.1.2.

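### Baseline WMH load is not named as a covariate for new-lesion progression, so an 'independent predictor' need not be independent of existing lesions

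*SAP*

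**What the plan says.** The SAP is one continuous section. The primary outcome is WMH progression at 18 months, "defined as the appearance of at least 1 new lesion on cerebral magnetic resonance imaging". The primary analysis is directed at "identifying independent predictors of WMH among clinical characteristics of the patients as well as plaque related variables". The plaque variables that it goes on to mention are volume, ulceration and neovascularization.

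On the multivariable model the SAP says: "A multivariate regression analysis was then performed to identify factors that independently influence the burden of WMH in terms of number and volume". The entry rule follows: "All variables associating to WMH burden with a $p<0.10$ will be included in the multivariable model". No time point is attached to burden, and no covariate is forced into the model.

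The main hypothesis is stated without reference to adjustment: "Our main hypothesis is that subjects with a high plaque burden will experience the highest progression of WMH". The sample size takes the "probability of progressing in terms of WMH in the high burden group to be 50" per cent, against about 15% in the others, with one third of patients in the high-burden group.

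The protocol's opening aim treats WMH "quantitatively as number and volume of lesions and as brain volumes, and progression over 18 months of follow up", so burden and progression are listed as separate things. Under 'Brain magnetic resonance imaging', "FLAIR lesion volume and number is reported for the whole brain and for each hemisphere separately". Baseline imaging is due within one month of enrolment, so baseline lesion number and volume will be available for every imaged patient.

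**The concern.** Neither document names baseline lesion number or volume as a candidate predictor, covariate or stratifier for progression. It is an imaging measure of the brain, so it is not obviously a clinical characteristic or a plaque variable. The p<0.10 rule does not settle the matter, because it screens against WMH burden and not against new lesions. If burden means baseline burden, baseline load is the dependent variable and cannot be its own covariate. If it means follow-up burden, the screen still does not address progression. Baseline load is therefore neither required nor excluded.

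What is at stake is the meaning of independence. Suppose patients with more plaque already have more lesions, and patients with more lesions tend to gain new ones. Plaque can then be significant in a model without baseline load even if it carries no information beyond the lesions already present. A reader would probably take an independent predictor of new lesions to mean more than that.

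**Working it through.** **1. The plan's own figure.** Inputs from the SAP: prevalence B = 0.33, p1 = 0.50, p2 = 0.15, alpha 0.05 (taken as two-sided), power 0.80. The overall rate is P = 0.67×0.15 + 0.33×0.50 = 0.2655. The formula for logistic regression on one binary predictor is

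N = [1.960·√(P(1−P)/B) + 0.842·√(p2(1−p2) + p1(1−p1)(1−B)/B)]² / [(p1−p2)²(1−B)]

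= (1.507 + 0.671)² / (0.1225×0.67) = 4.741 / 0.0821 = 57.8, so 58.

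The stated N reproduces with no allowance for any other covariate. With 19 high-burden patients and 39 others, expected events are 19×0.50 + 39×0.15 = 15.35. The planned odds ratio is (0.50/0.50)/(0.15/0.85) = 5.67.

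**2. Assumed inputs.** The documents give neither the correlation between plaque burden and baseline load nor the effect of existing lesions on new ones. Both are shown as ranges:
- r, the correlation of baseline load with *continuous* plaque burden: 0 to 0.5. With the planned top-tertile indicator, r = 0.1, 0.3 and 0.5 become about 0.08, 0.23 and 0.38.
- Log-odds of a new lesion per SD of baseline load: 0.5 to 1.1 (odds ratios of about 1.6 to 3.0).
- No plaque effect once baseline load is given; 15.35 expected events; likelihood-ratio tests; 20,000 simulated studies per scenario.

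**3. How often plaque is significant with no effect beyond existing lesions.**

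| r | No covariates | One screened clinical factor explaining half of r | Baseline load in model | Apparent plaque odds ratio, no covariates |
|---|---|---|---|---|
| 0 | about 6% | – | about 6% | – |
| 0.1 | about 6% | – | about 6% | 1.1–1.2 |
| 0.3 | 7–12% | 6–8% | about 6% | 1.3–1.6 |
| 0.5 | 10–23% | 7–11% | about 6% | 1.5–2.1 |

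If the clinical factor explains all of r, the rate is about 6%. The reference level is about 6%, not 5%, because of the test's small-sample behaviour.

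The two models disagree (significant without baseline load, not with it) in 3–8% of studies at r = 0.3 and 7–20% at r = 0.5. At r = 0.1 the figure is 1–2%, the same as at r = 0, so it is noise.

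**4. Cross-check with a binary baseline load.** Assume no plaque effect, 26.55% progression overall, and high baseline load in 30% of the lower-plaque group.
- If 50% of the high-plaque group have high load and it triples the odds, the risks are 0.295 and 0.251. The apparent odds ratio is (0.295/0.705)/(0.251/0.749) = 1.25.
- If 70% have high load and it raises the odds eightfold, the risks are 0.366 and 0.216, and the odds ratio is 2.10.

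This agrees with the upper end of the table.

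**5. Power of the baseline-adjusted test at N = 58.**
- If 50% and 15% are the unadjusted rates, as the SAP reads: about 77–81% (r = 0.1), 62–69% (r = 0.3) and 38–56% (r = 0.5). Reaching 80% would need about 57–60, 78–89 and 107–168 patients.
- If instead the adjusted odds ratio stays at 5.67: about 67–79%, with 60–78 patients needed for 80%.

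**The case against.** The best defence is that the SAP already says what independence is relative to: the clinical and plaque variables it lists. It never claims independence from existing lesions. Its main hypothesis concerns which patients progress most, which is an overall comparison. When r is above zero, high-burden patients in the simulation really do progress more often, so a significant unadjusted result is correct for that hypothesis. If plaque causes WMH, baseline load may be a mediator, and leaving it out is right for the total effect. The plan also foresees a multivariable model, and the protocol collects blood pressure, diabetes, lipids, smoking and a Framingham score that includes age, so the no-covariate rates overstate what the planned analysis would produce. Finally, the wording of the entry rule does not exclude baseline load.

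Most of this stands, and it limits the point. A reader might infer that the primary comparison is biased, or that its type I error rises to as much as 23%. The documents do not support that: the rates above are errors only for the narrower question of what plaque adds beyond existing lesions. A reader might also infer that baseline load is ruled out of the model, and it is not.

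What the defence does not remove is that independent predictors are the stated target of the primary analysis, that the most direct alternative explanation for new lesions is measured but not named, and that the only entry rule is tied to a different outcome.

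**Conclusion.** The point holds in a conditional form. As written, the search for independent predictors does not name baseline WMH load for new-lesion progression, and a plaque finding could be reported as independent when it adds nothing beyond existing lesions. The gap in the text is certain. Its consequence rests on two associations that the documents do not give. It is nil if plaque burden and baseline load are uncorrelated, immaterial at r = 0.1, modest at r = 0.3 and substantial at r = 0.5 only if clinical covariates explain little of the correlation.

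It would be too strong to say that the omission could produce the planned effect: over the ranges tried the apparent odds ratio is at most about 2.1, against 5.7. The sample size of 58 is also correct on its own inputs. The change is worth making, with medium confidence, as an added and labelled analysis and not as a correction of the main comparison.

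**What to change.** Keep the main hypothesis on the overall comparison, and add to the SAP:

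- One baseline term named in advance, for example log(1 + baseline lesion number), which is defined when there are no lesions.
- The logistic model of progression fitted without this term and then again with it, whatever its p-value.
- Both plaque odds ratios with 95% CIs, labelled *overall association* (without) and *association beyond existing lesions* (with). Plaque is described as independent of existing lesions only if the second estimate supports it.
- A statement that the 80% power applies only to the comparison without baseline load, and that a non-significant adjusted result at N = 58 is not evidence that plaque adds nothing.

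A milder option is to name baseline load as a candidate and screen it at p<0.10 against progression. That also keeps the rate at about 6%, but the meaning of the single reported odds ratio then depends on whether the term entered.

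The cost is SAP wording and one extra model, with no new data. There are three downsides. The second model spends one more parameter on about 15 events. Baseline load may be a mediator, which is why both estimates are needed. The adjusted test may fall well short of 80% power, and does so most where the correlation is strongest.
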